2. STUDY OBJECTIVES

Primary objective:

1. **To test if the DUO-EF algorithm can achieve a sensitivity and specificity above 80% for detection of LVEF above or below 40% in comparison to gold-standard echocardiography**

Secondary Objectives:

- To perform a subgroup analysis of DUO-EF against LVEF calculated by cardiac MRI (another gold standard investigation for calculating LVEF <40%)
- To validate consistency of DUO-EF result at point-of-care in GP practice ('real world' use where GP suspects new heart failure) against repeat DUO-EF at time of gold-standard investigation
- To validate consistency of DUO-EF result at point-of-care in Covid-19 follow up clinic ('real world' use where clinicians suspect new heart failure) against repeat DUO-EF at time of gold-standard investigation
- To measure if participants with DUO-EF suggestive of LVEF <40% but with gold standard investigations where LVEF >40% are at increased risk of developing heart failure at 24 months i.e. can DUO-EF predict future development of LVEF <40% at 24 months
- To evaluate DUO-EF point-of-care determination of LVEF<40% in comparison with the components of the established NICE primary care pathway (e.g. BNP result)

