3. STUDY DESIGN & METHODS

Statistical Considerations

Type of study: Prospective cross-sectional study comparing identification of LVEF above or below 40% by DUO-EF algorithm versus gold-standard methods.

Duration: Start date 01/02/2021, duration 36 months

Number and type of participants: across all settings 2,400 total

Sample Size

Imperial College Healthcare NHS Trust performs over 20,000 echocardiograms per year across its three hospital and community sites, serving the most ethnically and socioeconomically diverse population in the UK.

Based on established data and extensive clinical expertise of the investigators, around half of all patients who attend for echocardiography at the Trust are found to have LVEF <40%. **The sample size calculation below addresses the primary objective: evaluating if the DUO-EF algorithm can achieve a performance of sensitivity and specificity above 80% for detection of LVEF above or below 40% – compared to gold-standard echocardiography.**

SAMPLE SIZE CALCULATION

Primary Variable: Left Ventricular Ejection Fraction >/< 40%

Null Hypothesis: DUO-EF **DOES NOT** detect with sensitivity and specificity exceeding 80% a LVEF greater or less than 40%

Alternate Hypothesis: DUO-EF **CAN** detect with sensitivity and specificity exceeding 80% a LVEF greater or less than 40%

Type 1 error 5% (5% 2 sided test)

Type 2 error 20% (80% power)

Based on the above parameters for sample size calculation (Ref: G*Power, proportion, difference from a constant [binomial test 1 sample test]) to address the primary objective, this study will recruit participants until at least 500 have been recruited with an LVEF above 40% and 500 with a LVEF below 40% i.e the minimum total required is 1000 patients.

This will provide us with an ability to estimate sensitivity and specificity with a 95% CI $\pm 3.3\%$, and assuming the underlying sensitivity and specificity are at least 85% provide us with 80% power at the 5 % significance level to detect that they exceed the pre-specified criterion of a sensitivity and specificity of 80%.

Dropouts: Dropouts are unlikely within the context of the primary objective since consent and the entire data collection will occur within a short space of time during a single clinical visit (standard-of-care attendance for echocardiography).

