Protocol Allowances: Although we require 466 patients with EF >40% and 466 patients with EF <40% we have rounded these up to 500 patients. Furthermore, we will likely need to recruit up to 1,500 patients in total since it is unlikely that the first 1,000 patients will fulfil the exact breakdown of required LVEF above and below 40%.

Controls: The ‘control’ population in this study are participants with LVEF>40%. Indications for referral to echocardiography are broad and include but are not limited to: suspected or known

ischaemic heart disease, suspected cardiomyopathy, pericardial disease, murmurs, assessment of valve disease, assessment of prosthetic valves, assessing chronic lung disease, neurological disease (stroke or transient ischaemic attack), arrhythmia (palpitations and/or loss of consciousness), high blood pressure (common) and as a standard investigation considered before surgery. Many of these referred patients are found to have no abnormalities on echo and are otherwise healthy. Therefore, the unselected approach of this study to include all-comers to echo will generate a population sample that can be evaluated for alignment with the type of population in whom a screening programme for heart failure may be beneficial.

Performance characteristics: Eko Health (the 'manufacturer' of the algorithm) indicate a performance of 80% sensitivity and 80% specificity for the identification of LVEF above or below 40%

Confounders: our study design precludes confounders

Avoidance of bias for primary objective

To avoid any biases in both the recording of DUO-EF readings by the member of the research team and this influencing calculation of %LVEF by the echocardiography team (sonographer), the following steps will be taken:

- The member of the research team approaching patients in the echo department for consent will not be aware of the indication for referral at time-of-consent
- DUO-EF readings can happen before or after the echo, with the member of the research team unaware of the echo-derived %LVEF until they check the electronic health record (after DUO-EF has already been recorded).
- The sonographer will not be made aware of the results of DUO-EF, therefore not biasing any interpretation of %LVEF if borderline around 40%

Study Participant Population

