All study participants will be approached to take part and have a DUO-EF reading during the course of their routine care (minimal disruption) in the echo or cardiac MRI setting, during their GP appointment, or while attending COVID-19 follow up clinic. This will result in a large, representative study population to meet the objectives of testing the hypothesis for DUO-EF as a screening tool.

Group 1: Departmental Echocardiography and Cardiac MRI, Imperial College Healthcare NHS Trust

Unselected patients attending for departmental echocardiography (n = 1,500) and subgroup in cardiac MRI (n = 100). Patients will be consented by a member of the research team while they wait for an echocardiogram/cMRI. Patients from group 2 (GP referrals) will also be attending for an echo as part of their routine care on the heart failure pathway; they will be re-consented by a member of the research team upon arrival in the department.

Researchers will perform and record DUO-EF readings on participants and subsequently review echocardiography and cardiac MRI reports and document the LVEF calculated by these modalities.

If echocardiography does not suggest heart failure with LVEF<40% but DUO-EF does, patients will be followed-up with a **24 month phone call** (early evidence indicates the algorithm can identify low ejection fraction before being detectable on echo⁸).

Group 2: Patients in Primary care ('real world' evaluation)

NIHR North West London Primary Care **Clinical Research Network** (n = 10 GP practices). Patients attending GP with signs/symptoms of heart failure (n = 400 in total across all sites) will proceed with standard-of-care NICE heart failure pathway, with no change to standard of care through participation in study. GP's will be asked to record DUO-EF in any patient where heart failure is suspected.

Researchers will capture the point-of-care DUO-EF prediction from the GP:

- Comparing this to repeat DUO-EF ('agreement' between two time points) at time of (group 1) echocardiography (if indicated by standard of care investigations: BNP and 12-lead ECG)
- And comparing both of these DUO-EF measurements to echocardiography derived LVEF

Group 3: COVID-19 Clinic, Imperial College Healthcare NHS Trust

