4.2 INCLUSION CRITERIA & EXCLUSION CRITERIA

Inclusion criteria for all	
 - Age 18 years or above - Able to give informed consent 		
	Group 1	Group 2	Group 3
Additional inclusion criteria	
 - Patient attending for departmental echo or cardiac MRI 	
 - GP concerned about heart failure diagnosis and initiates patient onto routine NICE pathway 	
 - Attending COVID-19 follow-up clinic and clinician concerned about heart failure diagnosis and initiates patient onto routine NICE pathway
Exclusion criteria	
 - Any chest wound, skin pathology or other feature that would prohibit routine stethoscope examination 		

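### Group 1 does not separate patients with earlier low LVEF, so the 24-month outcome can count recurrence as predicted development, and pooled sensitivity alone does not support the screening-tool statement

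*Protocol*

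**What the plan says.** Protocol section 4.2 gives Group 1 one additional inclusion criterion, "Patient attending for departmental echo or cardiac MRI", besides adult age and capacity to consent. The only exclusion is "Any chest wound, skin pathology or other feature that would prohibit routine stethoscope examination". Section 3, Study Participant Population, describes the group as "Unselected patients attending for departmental echocardiography (n = 1,500) and subgroup in cardiac MRI (n = 100"). The Study Summary limits Groups 2 and 3 to patients whose symptoms newly suggest heart failure.

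Two statements concern screening. In Study Participant Population, after a sentence covering all recruitment settings, the protocol says: "This will result in a large, representative study population to meet the objectives of testing the hypothesis for DUO-EF as a screening tool". Under Controls, the echo sample is described more cautiously, as "a population sample that can be evaluated for alignment with the type of population in whom a screening programme" may help.

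For the longer term, section 2 asks "can DUO-EF predict future development of LVEF <40% at 24 months". Sections 3.1 and 6 apply this to all participants with a positive DUO-EF and a gold-standard LVEF above 40%, with no condition on earlier LVEF. The reason given in section 3 is that "early evidence indicates the algorithm can identify low ejection fraction before being detectable on echo".

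The list of health-record data in section 7 includes comorbidities and the LVEF from echo and cardiac MRI. It does not name an earlier LVEF.

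**The concern.** A patient returning for a repeat echo with established low LVEF enters Group 1 on the same terms as a patient with no cardiac history. Two conclusions are affected.

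The first is the 24-month outcome. A participant whose LVEF was once below 40% and has since improved, say to 45%, can be DUO-EF positive and gold-standard negative. If LVEF falls again, the event counts as development predicted by DUO-EF. The stated rationale is that the algorithm sees low LVEF before echo does. A low LVEF that an earlier scan had already shown is no evidence for that.

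The second is the screening statement. Screening and first diagnosis concern people not already known to have the condition. If sensitivity differs by prior status, the pooled figure from Group 1 is not the figure for them.

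**Working it through.** **The plan's own figure.** Section 3 tests 80% against an assumed true value of 85%, two-sided 5%, 80% power, and states 466 per LVEF class, rounded up to 500. An exact one-sample binomial test with an upper tail of 0.025 first reaches 80% power at n = 466 (reject at 390 or more; tail probability 0.0245; power 0.805). The figure reproduces. At n = 500 the test rejects at 418 or more (418/500 = 83.6%), with power 0.827. The arithmetic is sound; the question is whom the pooled proportion describes.

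**24-month outcome (no numerical assumption needed).**
1. Entry to Group 1 does not depend on earlier LVEF (section 4.2).
2. Entry to the follow-up set depends only on a positive DUO-EF and a current gold-standard LVEF above 40% (sections 3.1 and 6).
3. The event is a later LVEF below 40% (section 3.1).
4. A participant with earlier low LVEF, now improved, meets 1 and 2, and a relapse meets 3. No listed field identifies that participant.

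Participants whose current LVEF is below 40% never enter this set, so the problem is confined to previously low, now improved LVEF.

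Size of the set: with specificity 0.85 to 0.80, false positives number 500 × 0.15 = 75 to 500 × 0.20 = 100. If 750 participants with LVEF above 40% are recruited, they number about 113 to 150. Assume, for illustration only, a 24-month risk of 20% with earlier low LVEF and 5% without. The pooled risk is g × 0.20 + (1 − g) × 0.05, where g is the share with earlier low LVEF:

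| g | Pooled risk |
|---|---|
| 10% | 6.5% |
| 25% | 8.75% |
| 50% | 12.5% |

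The risk in those without earlier low LVEF is 5% throughout.

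**Pooled sensitivity.** Let f be the known share among 500 participants with LVEF below 40%. Then pooled sensitivity = f × S(known) + (1 − f) × S(not known). The protocol gives none of these three inputs. Assuming S(known) = 0.90 and S(not known) = 0.75:

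| f | Pooled sensitivity | P(at least 418 of 500) |
|---|---|---|
| 30% | 0.30 × 0.90 + 0.70 × 0.75 = 79.5% | 0.01 |
| 50% | 82.5% | 0.28 |
| 60% | 84.0% | 0.63 |
| 70% | 85.5% | 0.90 |

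Pooled sensitivity passes 80% when f exceeds (0.80 − 0.75)/0.15 = 33%, and reaches the rejection bound at (0.836 − 0.75)/0.15 = 57%. If the two sensitivities are equal, f has no effect. If they are reversed (0.75 known, 0.90 not known), f = 30% gives 85.5% pooled, which understates the not-known group.

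**Precision of the added estimate.** With sensitivity 0.80, the 95% half-width is 1.96 × √(0.16/n): 3.5 points for n = 500, 4.0 for 375, 5.0 for 250 and 7.0 for 125 (known shares of 0, 25%, 50% and 75%).

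**The case against.** The strongest reply is that the primary objective makes no claim about undiagnosed patients. It compares DUO-EF with echo, and all-comers is a legitimate population for that. This stands, and the primary analysis should not change.

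Next, the representativeness sentence follows one about all settings, and the Controls paragraph leaves alignment with a screening population to be evaluated. Groups 2 and 3 also bring suspected new disease: the Study Summary compares point-of-care DUO-EF with gold-standard ejection fraction in both. This stands in part. Those groups supply some accuracy data, but only for patients who go on to gold-standard imaging, and section 3.1 names only consistency of DUO-EF as their outcome. Alignment on prior status cannot be evaluated reliably unless it is recorded.

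A subgroup estimate can be left to the SAP, and comorbidities are already captured. But earlier LVEF is not a listed field, and the 24-month outcome is defined in the protocol itself.

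The protocol speaks of future development, not of first onset, and gives no count of patients with improved LVEF. That is so, but the rationale of detection before echo fits only patients in whom echo had not already shown low LVEF.

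A reader might infer more: that known cases have more marked ECG changes and are easier to detect, so the trial would declare success while sensitivity in undiagnosed patients is below 80%. The documents do not support this. Nothing in them says that sensitivity differs by history or gives the known share. The statement that "around half of all patients who attend for echocardiography at the Trust are found to have LVEF <40" per cent concerns prevalence and does not say how many were known before.

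**Conclusion.** The point holds in two parts of different strength.

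The 24-month part is a defect of definition that follows from the eligibility and outcome text alone: recurrence of earlier low LVEF counts as predicted development. How many participants it affects is unknown. It concerns one secondary outcome, in a set of roughly 75 to 150 participants under the specificities assumed above.

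The sensitivity part is a limit on interpretation, not a flaw in the primary test. The pooled estimate answers the primary objective. By itself it does not support the screening-tool statement, because sensitivity in patients without known low LVEF may be higher, lower or the same. The 90%, 75% and known-share figures are assumptions that show what could happen; they do not estimate what will. That known cases enter Group 1 at all is read from the absence of any criterion against them; no sentence says so outright.

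**What to change.** Keep the all-comers criterion, the primary analysis and the sample size, and make three changes.

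1. Add to the section 7 data list whether the health record shows an earlier LVEF below 40% or an earlier heart failure diagnosis. Extract it only after the DUO-EF reading is recorded. Section 3 keeps the researcher unaware of the referral indication at consent and of the echo LVEF until the reading is done; opening the record at entry would endanger both.
2. State in section 3.1 that sensitivity and specificity are also reported in participants without that history, and that any screening or diagnosis conclusion rests on this estimate.
3. Restrict the 24-month outcome to participants with no earlier LVEF below 40%, and report the others separately as recurrence.

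The cost is one record-derived field and one added estimate. The downside is lower precision in the subset (a half-width of 5.0 points instead of 3.5 at sensitivity 0.80 if half the low-LVEF participants are known) and a smaller 24-month denominator. A history that was never recorded will be missed, so the split will be imperfect.

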 - Development of LVEF <40% at 24 months in participants with initial DUO-EF suggestive of LVEF <40% but gold standard investigations LVEF >40% i.e., can DUO-EF predict future development of LVEF <40%
 - DUO-EF point-of-care determination of LVEF<40% in comparison with the components of the established NICE pathway (BNP result)

POPULATION

- **Group 1:** All-comers to **echocardiography** and cardiac MRI departments across Imperial College Healthcare NHS Trust (**echo n = 1,500**, cMRI n = 100)
- **Group 2:** Patients seen in primary care (GP) with symptoms newly suggestive of heart failure (n = 400); contributing to Group 1 if standard of care indicates need for referral to echo/cMRI
- **Group 3:** Patients seen in the COVID-19 follow-up clinic with symptoms newly suggestive of heart failure (n = 400); contributing to Group 1 if standard of care indicates need for referral to echo/cMRI

ELIGIBILITY

Inclusion criteria for all	
 - Age 18 years or above - Able to give informed consent 		
	Group 1	Group 2	Group 3
Additional inclusion criteria	
 - Patient attending for departmental echo or cardiac MRI 	
 - Attending for GP appointment; GP concerned about heart failure diagnosis and initiates patient onto routine NICE pathway 	
 - Attending COVID-19 follow-up clinic; clinician concerned about heart failure diagnosis and initiates patient onto routine NICE pathway

Exclusion criteria	Any chest wound, skin pathology or other feature that would prohibit routine stethoscope examination
---------------------------	--

DURATION Start date 01/02/2021, duration 36 months

[figure not shown]
STUDY WORKFLOW SUMMARY DIAGRAM ON NEXT PAGE

DUO-EF-19: Diagnosis of Heart Failure in the Post-COVID-19 Clinic, Primary Care and Hospital Setting Using a Digital Stethoscope with AI ECG

Study Workflow

[figure not shown]
Imperial NHS Trust Echocardiography and Cardiac MRI Departments

St Mary's, Hammersmith & Charing Cross Hospitals and Community Cardiology Centres

[figure not shown]
GP Practices

NIHR North West London Clinical Research Network portfolio support

COVID-19 Clinic

All-comers to COVID-19 follow up clinic at St Mary's Hospital

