Patients attending COVID-19 follow up clinic (n = 400). Only patients who are being routinely referred onto the heart failure pathway for investigations will be invited to participate i.e. patients **with clinical symptoms of heart failure**, who would/should be referred onto routine NICE pathway. Researchers will capture the point-of-care DUO-EF prediction from the Covid-19 follow up clinic setting:

- Comparing this to repeat DUO-EF ('agreement' between two time points) at time of (group 1) echocardiography
- And comparing point-of-care and time-of-echo DUO-EF results

Method for Single-Lead ECG Collection for DUO-EF

For echo and cMRI, DUO-EF recordings will be made after these gold standard investigations so as not to bias interpretation of results. The protocol for DUO-EF recording for all patients in the COVID-19 follow up clinic, GP, echo and cMRI setting will be as follows:

1. Clinical user turns on Eko DUO device and confirms connection to secure app
2. Participants sitting upright will have 15 second single-lead ECGs recorded by the Eko DUO from five different locations:
 - a. Lead I position (holding the device's electrodes between two hands)
 - b. Clavicle
 - c. Angled
 - d. V2 position
 - e. V5 position
3. Five recordings of DUO-EF recorded by researchers

The participant will be categorised as having a DUO-EF <40% if any of the five DUO-EF readings suggest this.

Data point collection: %LVEF echo, %LVEF cMRI, BNP

Recording %LVEF from echocardiography

EF is routinely measured or estimated using well-established standardized methodologies. For the purpose of this study we draw on previous work by Attia et al (2019) to record the %LVEF value on echocardiography using the first available model in a standard hierarchical sequence:

- EF determined using 3-D echocardiography¹²
- Biplane approach using the Simpson method¹³ a 2-D method, or M-mode
- In the absence of any of the preceding, the reported visually estimated EF

If the estimation is a range, the midpoint as a single LVEF value will be used. LVEF will also be classified as low ($\leq 40\%$), moderately depressed (41–49%), or normal ($\geq 50\%$).

Recording %LVEF from cardiac MRI

As with echo, standard approaches to calculating EF also exist for cMRI. Calculated %LVEF (reported as standard) will be recorded alongside classification as low ($\leq 40\%$), moderately depressed (41–49%), or normal ($\geq 50\%$).

Brain Natriuretic Peptide

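### Group 2 entry is worded two ways, and nothing puts the GP's pathway decision before the DUO-EF reading or masks the GP to it, so the index result could influence who is analysed

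*Protocol*

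**What the plan says.** **Group 2, when DUO-EF is read.** Protocol section 3, Study Participant Population, Group 2: "GP's will be asked to record DUO-EF in any patient where heart failure is suspected". Starting the pathway is not named there as a condition.

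**Group 2, who is eligible.** Section 4.2, and in near-identical form the Study Summary: "GP concerned about heart failure diagnosis and initiates patient onto routine NICE pathway". This has two conditions, concern and initiation.

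**Group 2, what follows.** The sentence before the recording instruction says that patients presenting with signs or symptoms "will proceed with standard-of-care NICE heart failure pathway, with no change to standard of care through participation in study". Repeat DUO-EF and echo come later, "if indicated by standard of care investigations: BNP and 12-lead ECG". The Study Summary has these patients "contributing to Group 1 if standard of care indicates need for referral to echo/cMRI".

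**Masking.** The steps in section 3 under Avoidance of bias for primary objective cover the researcher in the echo department and the sonographer. The GP is not mentioned. Section 5 states that DUO-EF does not interfere with standard of care.

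**Group 3.** Section 3: "Only patients who are being routinely referred onto the heart failure pathway for investigations will be invited to participate". The same sentence then describes them as patients "who would/should be referred onto routine NICE pathway". The Study Workflow carries the label "All-comers to COVID-19 follow up clinic at St Mary's Hospital".

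**The concern.** A patient in whom the GP suspects heart failure but does not start the pathway is measured under section 3 and ineligible under section 4.2. The protocol does not say whether that patient counts. The GP decides on the pathway and is also asked to record DUO-EF, so the test under evaluation may be read before the decision that makes the patient eligible.

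If a negative reading made a GP less likely to start the pathway in a borderline patient, DUO-EF-negative patients would be under-represented, both true and false negatives. Sensitivity in the real-world evaluation (Aim 2) would then be overstated and specificity understated. The mix of positives and negatives in the agreement and BNP comparisons would shift as well. The reference result for a patient never started on the pathway would usually not exist, so the loss could not be repaired at analysis.

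**Working it through.** **1. The margin at stake.** Section 3 tests 80% against an assumed 85%, two-sided 5%, 80% power, and requires 466 per LVEF class. An exact one-sample binomial test with upper-tail alpha 0.025 reaches 80% power first at n = 466 (reject at 390 or more, exact alpha 0.0245, power 80.5%). The figure reproduces and is not disputed. It shows that the study's working margin is 5 percentage points.

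**2. The order of steps in Group 2.**

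| Step | Where stated | Order fixed? |
|---|---|---|
| GP suspects heart failure | sections 3 and 4.2 | first |
| DUO-EF recorded | section 3, on suspicion | not placed before or after initiation |
| Pathway initiated | section 4.2, an entry condition | not placed before or after the reading |
| BNP and 12-lead ECG, then echo if indicated | section 3 | after initiation |

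BNP and ECG control the last step. They do not protect the initiation step.

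**3. Illustrative size.** Let s and p be true sensitivity and specificity, and w the fraction of DUO-EF-negative suspects not initiated because of the result. Two assumptions apply: w does not depend on true LVEF, and the later route to echo depends no further on DUO-EF. The documents give no value for w. I take s = p = 0.80, the manufacturer's figure in section 3.

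- Apparent sensitivity = s / [s + (1 − s)(1 − w)]
- Apparent specificity = p(1 − w) / [p(1 − w) + (1 − p)]

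| w | Sensitivity | Specificity |
|---|---|---|
| 0% | 80.0% | 80.0% |
| 10% | 0.80 / (0.80 + 0.18) = 81.6% | 0.72 / (0.72 + 0.20) = 78.3% |
| 25% | 0.80 / (0.80 + 0.15) = 84.2% | 0.60 / (0.60 + 0.20) = 75.0% |

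**4. Ceiling for the primary analysis.** Suppose all 400 Group 2 patients reached echo and counted within the 1,500, a weight of 400/1,500 = 0.267. With simple weighting, and the same LVEF mix in both parts:

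- w = 10%: 0.267 × 81.6 + 0.733 × 80 = 80.4% sensitivity; 0.267 × 78.3 + 0.733 × 80 = 79.5% specificity.
- w = 25%: 0.267 × 84.2 + 0.733 × 80 = 81.1% and 0.267 × 75.0 + 0.733 × 80 = 78.7%.

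This is a ceiling for each w. Fewer than 400 are likely to be referred, and the calculation treats the repeat reading at echo as always equal to the GP's reading.

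**The case against.** The strongest reply is that the two Group 2 wordings may describe the same patients. The background section presents BNP testing as what NICE advises once heart failure is suspected, so suspicion itself may be what starts the pathway. Section 3 says these patients proceed on it with care unchanged, and section 5 repeats that DUO-EF does not interfere. On that reading, a GP who withholds the pathway after a negative result departs from the protocol. This stands in part: selection by DUO-EF is an unguarded possibility, not a planned step. The statements are nevertheless assertions with no procedure behind them, and section 4.2 still lists initiation as a condition separate from concern.

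It is also unclear who sees the classification. Section 3 has researchers capture the prediction from the GP, but its recording method, common to all settings, has researchers record the five readings. Whether the GP sees the result before deciding is therefore open, not established. Nor does any text say that a non-initiated patient leaves the study. Section 7 retains all participants, but does not say whether such a patient is one.

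A reader might extend the mechanism to Group 3 and count 400 + 400 = 800 patients. The documents do not support that. Section 3 puts referral before invitation, hence before DUO-EF, and section 4.2 also requires initiation. The all-comers label sits beside a figure not shown and may only name the source clinic.

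**Conclusion.** The point holds for Group 2, at most 400 patients. Entry is stated two ways, the order of reading and pathway decision is not fixed, and the GP is not masked. The exposure is mainly in the real-world, agreement and BNP comparisons; the effect on the last two is not quantified here.

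The sizes are conditional. Shifts of +1.6 and −1.7 points (w = 10%) or +4.2 and −5.0 points (w = 25%) are not negligible beside a 5-point margin, but w is assumed, and w = 0 gives no bias.

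A reader might infer that the primary result is biased. That is not shown: the effect passes only through the unstated number of Group 2 patients referred to echo. Even at the ceiling of 400 it is about half a point at w = 10% and little more than one point at w = 25%. In Group 3 there is a wording inconsistency only. The change is worth making because it is specific and nearly free.

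**What to change.** 1. **One Group 2 entry definition**, used in the Study Summary, in section 3 and in section 4.2. If suspicion and initiation are meant as one event, say so.
2. **Fix the order.** The GP's pathway decision is entered in the record before DUO-EF is read. Alternatively, the GP is masked to the result until the decision is recorded.
3. **Report counts** of suspected, enrolled and echo-verified Group 2 patients by DUO-EF result, so that any selection is visible. Keeping non-initiated patients in the data set would not by itself repair sensitivity or specificity, because they would usually have no echo.
4. **Group 3, wording only.** Bring the all-comers label and the looser would/should phrase into line with the section 3 statement that only patients being routinely referred are invited.

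The cost is a wording amendment, a fixed order for two steps in one appointment, and a short table of counts. No extra visits or patients are needed and no clinical rule changes. The downside is slightly less flexibility in the consultation.
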